## 6.6. Withdrawal Criteria

Patients are free to stop study participation at any time without giving a reason. In the event of a participant's decision to withdraw from the trial, the Investigator should ascertain from which aspects of the trial the participant wishes to withdraw and record the details on the CRF. For participants withdrawing from all aspects of the trial, the investigator should ascertain from the participant if they continue to consent to collecting routine information from hospital records, and/or data linkage with existing databases e.g NHS Digital and eDRIS, cancer registries and national public health bodies.

Participants may withdraw from the trial intervention only; this may be at the discretion of the investigator due to safety concerns. If a participant is only withdrawn from the intervention, they must be followed-up in accordance with the protocol.

Participants moving away from the region of the local site should not automatically be withdrawn from the trial. Should this occur, please contact the Trial Office with details of the relevant participant, and they will endeavour to assign the participant's follow-up to a hospital site close to their new location. The participant's new contact address for postage of follow-up questionnaires, will also need to be updated with the Trials Office.

Participants who withdraw from the study after randomisation will not be replaced.

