#### **10.1. Sample Size Calculation**

Five-year disease free survival (DFS) for participants with node negative disease after NACT was around 80% based on the pooled analysis published by von MG et al [6]. With advanced drug treatment

and improved outcome over time we would anticipate higher rates of DFS to be seen today and thus the DFS in the control arm was estimated to be 90%. Thus, assuming five years recruitment and minimum of 4.5 years follow-up, recruiting 950 participants in each trial arm (1900 in total) would have the ability to demonstrate non-inferiority of omitting further axillary treatment, defining non-inferiority as 'no worse than 3.5%' below the control arm 5-year DFS with a 5% 1-sided significance level and 85% power, allowing for 7% non-collection of primary outcome data using the POWER procedure within the SAS statistical software.

Lymphoedema is a potential side effect of further axillary treatment and hence is considered as a coprimary endpoint. The AMAROS trial reported five year lymphoedema rates for ALND of 23% (76/328) and 11% (31/286) for ART [24] based on clinical signs of lymphoedema. A meta-analysis reported a lymphoedema rate for sentinel-node biopsy of 6% [3]. A minimum 5% important difference in the proportion of participants with lymphoedema is acceptable as defined by discussions with the clinicians, the PPI group and patient co-investigators. Any differences larger than this would provide stronger evidence and have a bigger impact on clinical practice. Thus assuming similar lymphoedema rates within this trial and the majority of participants randomised to standard axillary treatment had ART (rather than ALND) then a trial of 1900 participants would have 90% power to detect at least a 5% difference between trial arms if the overall lymphoedema rate in the control arm was 11%, with a 2sided significance level and allowing for 25% dropout. The allowance for attrition is greater as the outcome is participant-reported from questionnaires. The power would be higher to detect the larger differences between trial arms that would be expected with increasing use of ALND in the standard axillary treatment arm (see Table 1).

Table 1: Sample sizes for the proportion of participants self-reporting lymphoedema symptoms at 5 years using a 5% two-sided significance level and 90% power

Proportion in	Proportion in	Difference	Sample size	Total sample	Allowing for
control arm	no axillary		in each arm	size	25% dropout

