#### 10.3.3. Statistical Methods

Time to event outcomes, including the co-primary outcome of DFS, will be assessed using Kaplan-Meier curves and compared using Cox proportional hazards models. Hazard ratio (forest) plots will be constructed for the stratification variables and important prognostic factors. A sensitivity analysis will be carried out adjusting for stratification variables (institution, type of breast surgery, receptor status). Exploratory subgroup analyses will be performed for those having ALND or ART.

The proportion of patients experiencing lymphoedema at five years will be compared across trial arms using a chi-squared test and a logistic regression model used to adjust for stratification variables. Arm morbidity, arm function and QoL will be scored using the appropriate manuals and assessed using a longitudinal mixed model regression analysis if model assumptions valid or a standardised area-under-the-curve analysis. Consideration will be given to any missing data in the form of a sensitivity analysis to determine the degree to which the conclusions may change with different missing data assumptions and mechanism models.

All analyses will be carried out on an intention-to-treat basis to preserve randomisation, avoid bias from exclusions and preserve statistical power. Thus, all subjects randomised into the study regardless of whether they receive the study intervention will be analysed unless they withdrew consent for further follow-up. The success of no axillary treatment relies on the confirmation of both non-inferiority in DFS and at least a 5% reduction in the proportion of participants with lymphoedema. No adjustment for multiple testing has been incorporated.

A Statistical Analysis Plan (SAP) will be developed to provide full details of the planned analysis.

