## 10.6. Interim Analysis and Criteria for the Premature Termination of the Study

A formal interim analysis is planned when 33% of the required primary outcome events have been reported, which is anticipated to occur prior to recruitment closure. An overall 5% one-sided Type I error rate for testing non-inferiority will be controlled using an O'Brien-Fleming-like alpha-spending rule set at p = (0.01, 0.046) for the interim and final analysis respectively.

With a 5 year recruitment period, a minimum follow-up of 4.5 years, a 5 year estimated disease free survival of 90% in the control arm and 85% power, it is estimated that 282 DFS events are required for the final analysis; thus the formal interim analysis is planned when 93 DFS events have been reported. At this formal interim analysis, the trial may be stopped on the grounds of futility (i.e. conclude that it is not reasonably possible to show non-inferiority) if the obtained hazard ratio from the interim analysis is above the hazard ratio limit of 1.62 using a one-sided p-value of 0.01.

The Sponsor may suspend or prematurely terminate either the entire study, or the study at an individual site, for significant reasons that must be documented (e.g. an unacceptable risk to participants or serious repeated deviations from the protocol/ regulations). If this occurs the Sponsor shall justify its decision in writing and will promptly inform any relevant parties (i.e. participants, investigators, participating sites, REC, regulatory bodies).

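### DFS non-inferiority is to be judged by intention-to-treat alone, with no supportive adherence-based analysis, and the wording on withdrawn consent, read literally, removes randomised participants

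*Protocol*

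**What the plan says.** Section 10.3.3 (Statistical Methods) fixes the analysis basis for the whole trial: "All analyses will be carried out on an intention-to-treat basis to preserve randomisation, avoid bias from exclusions and preserve statistical power". It then says that all randomised subjects, whether or not they received the study intervention, "will be analysed unless they withdrew consent for further follow-up". The only sensitivity analysis named for time-to-event outcomes is adjustment for the stratification variables. Subgroup analyses for those having ALND or ART are labelled exploratory.

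The DFS hypothesis is non-inferiority. Section 10.1 says "the DFS in the control arm was estimated to be 90" per cent, with a margin of "no worse than 3.5" percentage points "below the control arm 5-year DFS with a 5% 1-sided significance level and 85% power". Section 10.6 adds that "it is estimated that 282 DFS events are required for the final analysis", with alpha "set at p = (0.01, 0.046) for the interim and final analysis respectively".

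Non-adherence is foreseen. Section 6.6 says "Participants may withdraw from the trial intervention only" and keeps such people in follow-up. Section 10.2 makes compliance with allocation one of the feasibility progression criteria, and the CONSORT diagram in section 10.3.2 counts those who did not receive their allocation. No crossover rate is stated, and the 7% allowance in section 10.1 is for uncollected primary outcome data.

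**The concern.** In a superiority trial, crossover shrinks the observed difference and makes a positive claim harder. In a non-inferiority trial the same shrinkage makes the claim easier. Controls who go without axillary treatment and experimental participants who receive it both move the observed hazard ratio towards 1. The three reasons given for intention-to-treat (keeping randomisation, avoiding exclusion bias, keeping power) do not address this.

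The word open-label is not applied to this trial, but no blinding is described. Section 6.3.2 has the allocation emailed to the site, and the comparison is surgery or radiotherapy against neither. Departures from allocation can therefore depend on knowing the arm, and so can withdrawal of consent. If those who withdraw were left out altogether, a post-randomisation exclusion related to arm could enter the analysis, and valid DFS time up to withdrawal would be lost.

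The trial's success rule requires DFS non-inferiority, and section 2 expects the results to change guidelines. A claim that owed something to non-adherence would carry into practice.

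**Working it through.** **Inputs from the protocol.** Control 5-year DFS 90%; margin 3.5 points, so 86.5% at the margin; 5% one-sided alpha; 85% power (all section 10.1); 282 events; final-analysis alpha 0.046 (section 10.6).

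**Reproducing the plan's figure.** Margin hazard ratio = ln(0.865)/ln(0.90) = 1.3765, with logarithm 0.3195. Schoenfeld events = 4 × (1.645 + 1.036)² / 0.3195² = 282, which matches. As a check on sample size, 1900 × 0.93 = 1767 participants with exponential DFS, 5 years' accrual and 4.5 years' minimum follow-up give 282.5 expected events at 90% against 86.5%.

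**Assumptions not in the protocol.** The crossover rate is varied. Crossover is unrelated to prognosis, and anyone who crosses over takes the DFS of the treatment received. The true effect lies exactly at the margin, so a correct test should accept non-inferiority 5% of the time.

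**Formulas.** Let x be the share of controls who go untreated and y the share of experimental participants who are treated.

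- Control DFS = (1 − x) × 0.90 + x × 0.865
- Experimental DFS = (1 − y) × 0.865 + y × 0.90
- Observable HR = ln(experimental DFS) / ln(control DFS)
- False non-inferiority rate = Φ[(0.3195 − ln HR) × √282/2 − 1.645]

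**Worked case, 10% each way.** Control DFS 0.8965, experimental DFS 0.8685, HR = 1.2904, ln HR = 0.2550. Then (0.3195 − 0.2550) × 8.396 − 1.645 = −1.10, and Φ(−1.10) is about 13.5%.

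| Crossover | Observable HR | False non-inferiority |
|---|---|---|
| None | 1.376 | 5.0% |
| 2% each way | 1.359 | 6.2% |
| 5% of controls only | 1.352 | 6.8% |
| 5% each way | 1.333 | 8.5% |
| 10% of experimental only | 1.338 | 8.0% |
| 10% of controls only | 1.327 | 9.0% |
| 10% each way | 1.290 | 13.5% |
| 20% each way | 1.210 | 28.6% |

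The rate reaches 10%, double the nominal level, at about 6.75% crossover each way, about 12% of controls alone, or about 15% of the experimental arm alone. At the final-analysis alpha of 0.046 it is 7.9% with 5% each way and 12.6% with 10% each way.

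**Simulation check.** Cox models in 4000 simulated trials per scenario (950 per arm, 7% dropout, about 293 events on average) gave 5.4% with no crossover, 8.7% with 5% each way and 14.2% with 10% each way. This agrees with the formula to within about one point.

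**The withdrawal wording.** Section 10.3.3 first gives avoidance of exclusion bias as a reason for intention-to-treat. Its next sentence makes analysis conditional on not having withdrawn consent for further follow-up. It does not say that these people are kept and censored.

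**The case against.** **Left to the SAP.** Section 10.3.3 defers full details to a SAP, where supportive analysis sets are commonly defined. That would answer a silent protocol. This one is not silent: it says all analyses are intention-to-treat, so a per-protocol analysis in the SAP would depart from it. The ALND/ART subgroup analyses may use treatment received, but they are exploratory and are not a per-protocol comparison of the arms.

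**Crossover may be small.** This stands as a limit on size. Compliance is a progression criterion and is reviewed by the Trial Management Group. Section 6.4.8.2 does not permit nodal radiotherapy in the experimental arm, and radiotherapy quality assurance is mandatory. A reader might infer that the false-claim rate will more than double. The protocol does not support that: permission to withdraw from the intervention says nothing about how often it happens, and at 1% each way the rate is only 5.6%. Crossover linked to prognosis could also change the size or direction of the effect.

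**The withdrawal clause may mean censoring.** DFS in section 3.2.1 runs to first event or the censor date, and section 6.6 asks those leaving the trial whether records and linkage may still be used. A reader might infer that collected data will be discarded. The text does not say so; it is only open to that reading.

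**Per-protocol analysis is biased too.** This also stands. The comparison is not randomised, and adjustment may not remove selection. A reader might conclude that both analyses must succeed, but that would put a non-randomised comparison into the decision rule.

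**Conclusion.** The point holds in a limited form. Intention-to-treat is a sound primary basis for a pragmatic comparison. The weakness is that the protocol makes it the only basis for a non-inferiority claim while foreseeing departures from allocation and assuming no rate for them. Under the stated assumptions, the 5% error rate becomes 6.2% to 13.5% for crossover of 2% to 10% each way. The actual inflation depends on adherence, which the protocol does not give. The withdrawal clause is an ambiguity that conflicts, on its literal wording, with the reason given for intention-to-treat; no loss of data is established. Both deserve correction before analysis, and neither invalidates the design.

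**What to change.** Make three changes in section 10.3.3.

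1. Keep intention-to-treat on all randomised participants as the primary DFS analysis.
2. Replace the exclusion with a statement that participants who withdraw consent for further follow-up remain in the analysis and are censored at the date of withdrawal.
3. Add a pre-specified supportive per-protocol DFS analysis: control participants who received ALND or ART, and experimental participants who received neither. Adjust for the minimisation factors and prognostic baseline factors. Report it beside intention-to-treat, and discuss any discrepancy when non-inferiority is interpreted, without making it a second formal gate.

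The cost is one extra analysis on data already planned: section 10.4 has axillary treatment recorded on the CRF. The downside is that this analysis is not fully protected by randomisation, which is why it supports the primary result and does not decide it. Sample size and treatment are unchanged.

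### The success rule asks for at least a 5-point lymphoedema reduction, but the stated 90% power is for a test of zero difference at a true 5-point effect

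*Protocol*

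**What the plan says.** Protocol section 10.3.3 (Statistical Methods) fixes the decision rule: success requires confirmation of "both non-inferiority in DFS and at least a 5% reduction in the proportion of participants with lymphoedema". The same section says that lymphoedema at five years will be "compared across trial arms using a chi-squared test and a logistic regression model used to adjust for stratification variables".

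Protocol section 10.1 (Sample Size Calculation) says of the 5-point figure: "A minimum 5% important difference in the proportion of participants with lymphoedema is acceptable". It then states that "a trial of 1900 participants would have 90% power to detect at least a 5% difference between trial arms", for a control rate of 11% and a rate of 6% without further axillary treatment, after 25% dropout. Table 1 gives 691 per arm for that case, at a two-sided 5% level and 90% power, or 1846 in total after dropout. The section adds that power would be higher with more use of ALND in the control arm.

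The protocol does not say whether the 5 points in the rule apply to the point estimate or to a confidence limit. It states no joint power for the two co-primary outcomes.

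**The concern.** A chi-squared test asks whether the two proportions differ at all. The rule in section 10.3.3 asks for a reduction of at least 5 points. These are different hypotheses, and the second is much harder to satisfy when the true reduction is exactly 5 points, which is the case the trial is sized on. The 90% would then describe a test that does not decide success.

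This rule is how the co-primary result will be declared. Followed literally, a trial with DFS non-inferiority and a statistically clear lymphoedema reduction of, say, 4 points would not count as a success. The other risk is that the meaning of the sentence is settled only after the data are known.

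**Working it through.** **Inputs** (Protocol section 10.1 and Table 1): control rate 0.11; rate without axillary treatment 0.06; two-sided 5% level; 1900 participants randomised 1:1; 25% dropout. Evaluable: 1900 × 0.75 = 1425, about 712 per arm. The 5% is read as percentage points, as in the Difference column of Table 1.

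**1. Reproducing Table 1.** The usual two-proportion formula for a null of zero difference gives 652 per arm. With continuity correction it gives 692, against 691 stated. Then 2 × 692 / 0.75 = 1845.3, rounded up to 1846 as stated. The other rows come to 509, 395, 318 and 264, against 509, 395, 319 and 264 stated. Table 1 is therefore a zero-difference calculation, and it is correct as such.

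**2. Power for significance at 712 per arm.**
- SE under the null = √(2 × 0.085 × 0.915 / 712) = 0.01478
- SE under the alternative = √((0.11 × 0.89 + 0.06 × 0.94) / 712) = 0.01472
- Power = Φ((0.05 − 1.96 × 0.01478) / 0.01472) = Φ(1.43) = 92.3%, or about 91% with continuity correction

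The stated 90% holds for this test.

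**3. Chance of meeting the written rule at 11% v 6%.**
- Point estimate of at least 5 points: Φ((0.05 − 0.05) / 0.01472) = Φ(0) = 50%. Exact binomial enumeration gives 50.3%, and the same 50.3% when p < 0.05 is also required.
- Lower 95% confidence limit above 5 points: Φ(0 − 1.96) = 2.5%.

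**4. The gap between the two criteria.** With the experimental arm observed at 6%, the smallest significant reduction d solves d = 1.96 × √(2p(1 − p)/n), where p = (0.12 + d)/2. This gives 2.7 points at 712 per arm and 2.8 at 691. Reductions from there up to 5 points are significant but fail the rule on the point estimate. At the design case this happens in 92.3% − 50% ≈ 42% of trials.

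**5. Sensitivity to the control rate** (other arm 6%, 712 per arm). Point-estimate power is Φ((d − 0.05)/SE). Confidence-limit power is Φ((d − 0.05)/SE − 1.96).

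| Control rate | Point estimate ≥ 5 points | Lower 95% limit > 5 points |
|---|---|---|
| 11% | 50% | 2.5% |
| 12% | 75% | 10% |
| 13% | 90% | 25% |
| 14% | 97% | 48% |
| 15% | 99% | 70% |
| 17% | >99% | 95% |

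For 90% power the control rate must be about 13.0% on the point estimate or 16.3% on the confidence limit.

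**6. Joint success at 11% v 6%,** using the stated 85% for DFS and assuming the outcomes are independent (my assumption): 0.85 × 0.50 ≈ 43% on the point-estimate reading, against 0.85 × 0.90 ≈ 77% if significance alone is meant.

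**The case against.** **The sentence may be shorthand.** Section 10.1 uses nearly the same phrase for the design effect: "would have 90% power to detect at least a 5% difference between trial arms". The primary objective in section 3.1 asks only that omission reduces the risk of lymphoedema, with no threshold, and the planned test is chi-squared. If 5 points is just the planning effect, 90% is the right power. This reading is possible, so a hard threshold cannot be taken as certain. But section 10.3.3 does not say it, and section 10.1 calls 5 points a minimum important difference. If shorthand was meant, the sentence still needs correcting.

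**The threshold may be deliberate.** Section 10.1 says the 5 points were agreed with clinicians, the PPI group and patient co-investigators. Refusing to call a 3-point gain a success would then be a legitimate choice. A point-estimate threshold set at the true effect always gives 50%; that is a property of the rule. This stands, so dropping the threshold is not the only acceptable repair. It does not rescue the 90%, which would still belong to another test.

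**11% is the lowest planning case.** Section 10.1 ties it to most controls having ART. Mixing its rates of 23% (ALND) and 11% (ART), a 25% ALND share gives 0.25 × 23 + 0.75 × 11 = 14%, and a 50% share gives 17%. The survey in section 2 found 79% of responding hospitals performing ALND and 9% ART, and at that split both readings exceed 99.9%. This is real mitigation, with limits: section 2 also cites 2019 guidance advising ART, and the 23% and 11% come from clinical signs, not self-report. The 90% is also claimed specifically at 11%.

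**What a reader might infer too readily.** One might conclude that Table 1 is wrong or the trial too small; Table 1 reproduces. One might also conclude that a promised joint power has been missed; the protocol states none.

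**Conclusion.** The point holds as a mismatch between a stated decision rule and a stated power. At the protocol's own design case, the lymphoedema half of the rule has about 50% power on the point estimate or 2.5% on the confidence limit, where 91-92% applies to significance alone.

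These figures rest on true rates of 11% and 6%, 25% dropout, and 5% read as percentage points. The 50% is the more lenient of the two literal readings. The shortfall is largest at 11%. On the point-estimate reading it is essentially gone at a control rate of 13%; on the confidence-limit reading it persists until about 16%.

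A reader might infer that the trial will probably fail its rule. The documents do not support that, because the control rate depends on an ALND share that is not fixed. They support only that the 90% is not the power of the rule as written, and that the rule does not say how it is to be judged.

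**What to change.** Make the success rule and the power statement agree, by one of two routes:

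- **(a) If 5 points is only the planning effect,** reword section 10.3.3 so that success is DFS non-inferiority together with a significantly lower lymphoedema proportion at five years (two-sided 5%). Report the risk difference with its 95% confidence interval against 5 points. The 90% in section 10.1 then stands.
- **(b) If 5 points is a deliberate threshold,** say in section 10.3.3 whether it applies to the point estimate or to the confidence limit. Replace the 90% in section 10.1 with the power of that rule (50% or 2.5% at 11% v 6%), and give values across control rates as in the table above.

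Under either route, state the joint power of the two co-primary outcomes and the assumption behind it. The cost is one sentence in section 10.3.3 and, under (b), a restated power in section 10.1. Sample size and data collection do not change. The choice should be fixed before lymphoedema is compared between arms.
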